Morbidity of second stage cesarean sections before and after provider completion of simulation education at Regions Hospital

NCT Number: NCT03387189

Document Date: July 30, 2019

1. Summary

Cesarean deliveries performed during the second stage of labor can be very difficult due to impaction of the fetal head deep in the maternal pelvis and is associated with increased risk of both maternal and perinatal complications. On preliminary review, 16% of cesarean deliveries at Regions Hospital since 1/1/2017 were performed during the second stage, making this a common situation encountered by obstetricians. There is little existing data to inform management of deeply impacted fetal heads, therefore these situations can be difficult for surgeons and other healthcare staff when they arise. Our study aims to determine the morbidity of second stage cesarean deliveries before and after implementation of simulation protocols that address delivery of the impacted fetal head for Ob/gyn surgeons, nursing staff, and surgical technicians at Regions Hospital.

2. Study Aims

The primary aim of this study is to assess change in maternal and perinatal morbidity of second stage cesarean section during the time periods before and after simulation education for Ob/gyn surgeons, nursing staff, and surgical technicians at Regions Hospital compared to change in these same metrics during the same time frame at Methodist hospital, where the simulation education is not occurring. The simulation protocol is a Quality Improvement activity that addresses delivery of the impacted fetal head in second stage cesarean section.

- Research question 1.1: Does implementation of a simulation protocol decrease a composite variable of maternal morbidity defined as a) extension of uterine incision, b) operative blood loss > 1000 mL c) requirement of transfusion, d) wound infection within 6 weeks, and d) endometritis within 6 weeks, at Regions Hospital compared to morbidity over the same time period at Methodist Hospital?
- Research question 1.2: Does implementation of a simulation protocol decrease a composite variable of infant morbidity defined as a) 5 minute APGARs <7, b) NICU admission, c) umbilical cord arterial pH <7.1, and d) fetal injury of cesarean delivery during the second stage of labor at Regions Hospital compared to morbidity over the same time period at Methodist Hospital?

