Members of the study team have verified the accuracy of this method of identifying cesarean section during the second stage of labor by cross-checking a Clarity pull of EMR data with chart audit for a random sample of 10 patients.

Medical staff inclusion criteria: all 120 staff members (staff physicians, residents, nurses, surgical technicians) at Regions hospital who practice in the Birth center who underwent required simulation education regarding delivery of deeply impacted fetal heads during second stage cesarean section (50 physicians and 65 nurses and 5 techs) and completed the surveys as part of the QI simulation project.

ii. Sample size

Patients: A data pull conducted by an HP Institute RIIS programmer in September 2017 indicated that there are 80 patients per year at Regions hospital having second stage cesarean sections and 80 patients per year at Methodist hospital having second stage cesarean sections. This study will gather data via programming and chart audit on the following counts of patients in these time period:

- A. July 1, 2014 – June 30, 2015 (80 Regions patients)
- B. July 1, 2015 – June 30, 2016 (80 Regions patients)
- C. July 1, 2016 – December 31, 2017 (120 Regions, 120 Methodist) - 18 mo PRE period
- D. January 1, 2018 – June 30, 2019 (120 Regions, 120 Methodist) - 18 mo POST period

Different subsets of patients will be used for different research questions. For research questions 1.1, 1.2, 2.2 Group C above will serve as the pre-period patients and Group D for post-period patients. Thus, the total patient sample size for these research question is expected to be n=480. For research question 2.3, in addition to Groups C and D, we will also include utilize the 160 patients from Regions in Groups A and B for a sample size of 400 at Regions and 240 at Methodist (n=640 total).

Medical staff sample size: The simulation center staff will survey 120 staff (50 physicians, 65 nurses, and 5 techs) immediately before and after the required simulation education as part of an existing QI project. This QI project data will be used to address

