Length of stay	EMR	Secondary Study endpoint	Continuous
Time from skin incision to delivery or uterine incision to delivery	Chart	Secondary Study endpoint	Continuous
Head pushed up from below prior to c/s	Chart	Relationship to morbidity outcomes	Binary
Previous c/s	Chart	Description	Binary
Extension of uterine incision	Chart	Component of Primary maternal study endpoint	Binary
Operative blood loss (codes as < 1000 mL vs. > 1000 mL for primary endpoint)	Chart	Component of Primary maternal study endpoint	Continuous, binary
Number of blood transfusions (coded as 0 vs. any for primary endpoint)	Chart	Component of Primary maternal study endpoint	Continuous, binary
Endometritis within 6 weeks postpartum	EMR	Component of Primary maternal study endpoint	Binary
Wound infection within 6 weeks postpartum	EMR	Component of Primary maternal study endpoint	Binary
UTI during maternal admission	EMR	Secondary study endpoint	Binary
Bladder/ureteral/urethral injury	Chart	Secondary study endpoint	Binary
Type of uterine incision made	Chart	Description	Continuous
Maternal discharge Hemoglobin	EMR	Secondary study endpoint	Continuous
APGAR score at 5 minutes (coded as <7 vs. >=7 for primary endpoint)	EMR	Component of Primary infant study endpoint	Continuous, binary
APGAR score at 1 minute	EMR	Secondary study endpoint	Continuous

NICU admission	EMR	Component of Primary infant study endpoint	Binary
Umbilical artery pH <7.1	Chart	Component of Primary infant study endpoint	Binary
Fetal injury (fractures, head injury, brachial plexus injury)	EMR	Component of Primary infant study endpoint	Binary
Fetal death	EMR	Secondary study endpoint	Binary
Fetal hyperbilirubinemia	EMR	Secondary study endpoint	Binary
Uterine incision to delivery time (also categorized as <1 minute >=1 minute)	Chart	Secondary study endpoint	Continuous
Maternal discharge hemoglobin	Chart	Secondary study endpoint	Continuous
Medical staff confidence in handling second stage cesarean sections	QI Project Staff Survey	Secondary study endpoint	Continuous
Medical staff perceptions of second stage cesarean sections	QI Project Staff Survey	Secondary study endpoint	Continuous
Medical staff knowledge of interventions & medications for second stage cesarean sections	QI Project Staff Survey	Secondary study endpoint	Continuous
Medical staff teamwork when handling second stage cesarean sections	QI Project Staff Survey	Secondary study endpoint	Continuous

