Staff survey: The pre and post staff surveys are used for the QI project to assess staff perceptions of the required simulation training, and are included as the end of the narrative as appendices. These surveys use items developed for this project rather than existing tools. Surveys include a label to identify whether they are gathered before or after the simulation, and contain items such as confidence in handling second stage cesarean sections.

f) Statistical analysis plan

Descriptives (mean, standard deviation, proportion) and frequency distributions of all variables will be computed and examined for distribution shape, outliers, missing data, and implausible data. Tables of descriptive statistics summarizing patients in both care systems (Regions, Methodist)

will be created. Because there are only 2 primary outcomes (both of which are composite variables), there will be no control for multiple testing. Inferential analysis of secondary endpoints will be considered exploratory with the known limitation that multiple testing could yield type 1 errors. Covariates in regression analysis will be specified a-priori on the basis of theory and when such covariates are unbalanced in comparison groups.

Research question 1.1: Does the simulation protocol decrease a composite variable of maternal morbidity defined as a) extension of uterine incision, b) operative blood loss > 1000 mL, c) requirement of transfusion, d) wound infection within 6 weeks, and d) endometritis within 6 weeks, at Regions Hospital compared to morbidity over the same time period at Methodist Hospital?

Analytic sample: 480 maternal patients (120 Regions before/120 after simulation; 120 Methodist before/120 after simulation). Each sample of 120 is viewed as an independent sample.

Analytic approach: Logistic regression will be used to predict the composite maternal morbidity endpoint (0/1) from hospital (Regions, Methodist), time (pre or post simulation), and their interaction. Covariates will be included if needed as described earlier. Model-based proportions, standard errors, and 95% CIs for each hospital for each time point, change over time, and differential change over time by hospital will be computed. A significant hospital * time interaction and pattern of effects showing more improvement over time in Regions than Methodist will support the underlying hypothesis of differential improvement over time favoring Regions and potentially due to the effects of the simulation.

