providers from other groups performing cesarean sections. Residents are consistent over a period of 4 years. The Regions Hospital birth center has protocols for cesarean sections that are standard for all patients undergoing this procedure. The study outcomes should be easily compared without variations in cesarean section protocol. At Regions Hospital, team simulation events are organized with the simulation center staff throughout the year for other obstetrical emergencies such as shoulder dystocia, postpartum hemorrhage and hypertensive emergencies. We have the support of the birth center administration for this study

6. Risks and Benefits

There should not be risks to mothers, babies, and providers with this study. There is minimal risk to conducting this study; it is a retrospective, data-only study.

Benefits may include:

Knowledge of whether simulation training improved maternal and perinatal outcomes in patients with deeply impacted fetal head at cesarean section, staff and provider teamwork, and staff and provider morale.

7. Data Confidentiality and Privacy

Data will be stored on secure servers with limited access. Servers are in a physically secure location on campus and backed up nightly. Data will also be protected by username and password requirements.

Data will be kept separately from patient identifiers. Identifiers will be destroyed at the earliest opportunity and data shared with the statistician will be completely de-identified.

Patient identifiers will not be printed at any time during the study.

8. Timeline

Mid October-mid December 2017: QI project. Hold 6 simulation events for the impacted heat at cesarean section scenario. Each scenario will be 2 hours in length and mandatory for all Regions Hospital birth center providers, residents, nursing staff and techs. Will administer pre and posttest questionnaire before and after simulation event.

December 2017- June 30th 2019: Study data extraction via Epic and chart review, from charts of patients undergoing second stage cesarean sections from pre and post simulation time periods.

June 2018: QI project. Administer staff questionnaire 6 months after simulation event.

June 2019: Data and statistical analysis and presentations and manuscript write up.

9. Dissemination/Sharing Results/Integration and Impact

Submit manuscript to peer reviewed journal

Research poster at the GME event in May 2018 and 2019

Resident research presentation May 2019

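### The timeline ends data extraction on the last delivery date, so late post-period women lack a full 6-week window for two of the five maternal composite components; the effect is small and cheap to avoid

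*Combined protocol and SAP*

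**What the plan says.** All references are to the combined protocol and SAP.

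- **Deliveries (section 4.b.ii, Sample size).** The post period is "D. January 1, 2018 – June 30, 2019 (120 Regions, 120 Methodist) - 18 mo POST period".
- **Endpoint (section 4.d, variable table).** Two of the five maternal composite components carry a follow-up window: "Wound infection within 6 weeks postpartum" and "Endometritis within 6 weeks postpartum". Both have the EMR as data source. The other three (uterine extension, blood loss, transfusion) come from chart review and carry no stated window.
- **Extraction and analysis (section 8, Timeline).** Extraction is given as "December 2017- June 30th 2019: Study data extraction via Epic and chart review, from charts of patients undergoing second stage cesarean sections", covering both pre and post periods. The analysis line reads "June 2019: Data and statistical analysis and presentations and manuscript write up".
- **Analysis (section 4.f, research question 1.1).** The composite is a 0/1 outcome in a logistic regression with a hospital-by-time interaction. The plan also reports "Model-based proportions, standard errors, and 95% CIs for each hospital for each time point, change over time", and differential change by hospital.
- **Document date (title block).** "Document Date: July 30, 2019".

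Section 4.c.ii allows for several data pulls, but words them as serving patient identification and gives no date after 30 June 2019. The plan states no lag after the last delivery, no later pull of outcomes, and no rule for a woman with under 6 weeks of follow-up.

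**The concern.** The last day of accrual is also the last day of extraction, so the last 6-week window closes on 11 August 2019, six weeks after the stated end of extraction. An infection not yet in the record would most likely appear in an EMR pull as no event rather than as a missing value. The planned look at missing data in section 4.f might therefore not reveal it.

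Post-period morbidity would then be slightly understated at both hospitals. That matters in two places:

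- The within-hospital change over time, which the plan reports. Under-ascertainment in the post period alone makes it look a little more like improvement.
- The infection components analysed singly under research question 2.2 (exploratory), where the loss is not diluted by the other three components.

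The key comparison, differential change between hospitals, is exposed only to the extent that the loss differs between hospitals.

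**Working it through.** **Inputs from the document.** 80 patients per year per hospital; post period 1 January 2018 to 30 June 2019; pre period 1 July 2016 to 31 December 2017 (section 4.b.ii); 6 weeks = 42 days (section 4.d); extraction from December 2017 to 30 June 2019 (section 8); composite rate of 20% if components overlap completely and 40% if they do not (section 4.g).

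**Inputs assumed.** Uniform accrual. Infection rate 5-15%, because the document gives none. Missed infections coded as absent.

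**The plan's own count.** 80 × 1.5 years = 120 per hospital, as stated.

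**Share with an incomplete window**

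- Post period: 546 days. Last window closes 30 June 2019 + 42 days = 11 August 2019.
- Pull on 30 June 2019: the last delivery with a full window is 19 May 2019. Incomplete: 20 May to 30 June = 42 days. 42/546 = 7.7%; 120 × 0.0769 = 9.2 women per hospital.
- Pull on the document date, 30 July 2019: the last full window is for 18 June. Incomplete: 19 to 30 June = 12 days. 12/546 = 2.2%; 120 × 0.0220 = 2.6 women per hospital.
- Pull once the last window has closed on 11 August 2019: none.

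**Understatement of the post-period composite (pull on 30 June, no overlap with other components)**

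Women delivered on 20 May lose 1 day of the window and those delivered on 30 June lose 42. The mean loss is 21.5/42 = 51%, taken as half if infections are spread evenly over the window.

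| Assumed infection rate | Half missed: 100 × rate × 0.5 × 0.0769 | All missed: 100 × rate × 0.0769 |
|---|---|---|
| 5% | 0.19 points | 0.38 points |
| 10% | 0.38 points | 0.77 points |
| 15% | 0.58 points | 1.15 points |

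**Against the standard error of a within-hospital change.** SE = √(2p(1−p)/120). No overlap corresponds to the 40% composite in section 4.g, so SE = √(2 × 0.4 × 0.6/120) = 6.32 points. Largest case: 1.15/6.32 = 18% of one SE. With complete overlap (the 20% composite), every infected woman is already positive on another component and the shift goes to zero.

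**Against the standard error of the difference in changes.** SE = √(4p(1−p)/120) = √(4 × 0.4 × 0.6/120) = 8.94 points. Equal infection rates at the two hospitals cancel on this scale. With 5% at one hospital and 15% at the other, the residual is 100 × 0.10 × 0.0769 × 0.5 = 0.38 points (half missed, 4% of one SE) or 0.77 points (all missed, 0.77/8.94 = 9%).

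**On the log-odds scale of the planned model.** Suppose infection-only events are 25-50% of composite events at both hospitals and half to all are missed in the affected group. Across the three planning scenarios in section 4.g, the interaction moves toward zero by 0.003 to 0.036 of its SE. The largest shift, at 40% v 23% with a 50% share and all missed:

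- Observed post rates are 0.40 × (1 − 0.5 × 0.0769) = 0.3846 and 0.23 × (1 − 0.5 × 0.0769) = 0.2212.
- The log odds ratio goes from −0.803 to −0.789.
- SE = √(3/(120 × 0.4 × 0.6) + 1/(120 × 0.23 × 0.77)) = 0.389, so the shift is 0.036 SE.

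**Possible offset in the pre period.** The last pre-period window closes on 31 December 2017 + 42 days = 11 February 2018, and extraction starts in December 2017. A pull of late pre-period charts on 31 December 2017 would cut short 42/549 = 7.7% of that period and nearly cancel the tilt. Pull dates are not given.

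**The case against.** The strongest reply is that section 8 is a coarse list of milestones, not a data lock. It puts analysis and manuscript writing in the month in which deliveries and extraction are still running, so it may only mark a start. The document is dated a month after the stated close and still carries these lines. They are therefore weak evidence of when the infection data were pulled, and the affected share could be 7.7%, 2.2% or zero. This stands: the point concerns the schedule as written, and the document does not show that any data were cut short.

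A second reply is that the endpoint definition itself requires 6 weeks, that section 4.d has the programmer document codes as work proceeds, and that missing data will be examined. This stands in part. The definition needs the window, but the only stated schedule does not allow for it, and nothing says how an incomplete window is handled. That such women would be coded as event-free remains an inference.

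A third reply concerns size. A reader might set the 1.15 points against the SE at a 20% composite (5.16 points) and call it 22% of one SE, or set the 0.77-point interaction residual against 7.30 points and call it 11%. Section 4.g ties the 20% rate to complete overlap, where the shift is zero, so those pairings contradict the plan. The consistent figures are 18% and 9%. Even these need every infection in the affected group to be missed, including for a woman delivered on 20 May with 41 of 42 days elapsed.

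A reader might also infer that the cut-off favours the simulation in the primary test. The document does not support that: both hospitals share the dates, and with equal infection-only shares the shift is toward no effect.

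**Conclusion.** The concern holds as a low-severity inconsistency in the schedule. As written, 7.7% of post-period delivery days have an incomplete window for two of the five maternal components. This is the share with incomplete follow-up; it should not be read as a share misclassified. Under the assumptions above, the post-period composite is understated by 0.19-0.58 points if half of the infections are missed and by at most 1.15 points if all are. That maximum is about 18% of one SE of a within-hospital change. It shrinks if infections appear early, overlap with other components, or are offset by early pre-period pulls. For the infection components taken singly, the relative understatement is 0.5 × 7.7% = 3.8% (half missed) to 7.7% (all missed).

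The primary hospital-by-time interaction is nearly unaffected: at most about 9% of one SE even with 5% v 15% infection and all missed. No primary conclusion is likely to change. Confidence is medium, because the actual pull date and the coding of incomplete windows are not stated.

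**What to change.** Change the section 8 timeline in three ways:

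1. Pull wound infection and endometritis from the EMR for all pre- and post-period women at both hospitals on one date, after 11 August 2019 plus coding lag. Using one date also removes any shortfall from early pulls of late pre-period charts.
2. Keep patient linkage until that pull is done. Section 7 has identifiers destroyed as soon as possible, and without them a later pull may not be matched to study records.
3. Start the primary analysis only after that pull.

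If a qualifying pull has already been made, stating its date is enough.

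The cost is about six weeks' delay (30 June to 11 August) plus coding lag, one further programmatic pull, and slightly longer retention of identifiers. Both items come from the EMR, so no extra chart review is needed, and the expected 120 per group is kept. The alternative of ending post-period deliveries on 19 May 2019 would keep the 30 June close but leave 504/546 × 120 = about 111 per hospital, which is the worse trade.
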